### **Strengths and limitations**

One strength of this study includes the 24/7 availability of the CCRC Research Intern and the ED Clinical Pharmacist to assist with patient enrollment. This will allow patients to be enrolled on all shifts. The biggest strength in this study is the potential to provide a data set more than double the size of the previous studies on early basal insulin administration in DKA. This study will also follow the patient throughout their hospital stay and look at potential practice changes to decrease the overall length of stay for patients with DKA. We have worked with all relevant departments (ED, Critical Care, Endocrinology, Pharmacy) to ensure that this research will fit into the current workflow for DKA patients without impeding patient care.

The biggest limitation is that while our sample size is larger than the previous publications on this topic, it is still a small pilot study and effects will be somewhat limited to our local setting and practices. This is also a single-center study and not all Emergency Departments have 24/7 ED Clinical Pharmacists available so these practices may not be easily duplicated. Not all patients who are eligible will agree to be in the study, which may cause participation bias. To avoid research bias, a staff member who will not be involved in consent will set up the randomization scheme, so enrollers will be unaware of the next randomization assignment when they approach patients

Furthermore, since this is a pragmatic study in the real-world setting of a functioning, busy ED, research has limited control over components such as timing of standard of care labs and study intervention. We will report and statistically correct for any large variation in timing of outcome labs, such as post-intervention glucose checks.

### **Setting/Environment/Organizational feasibility**

The study will be conducted at Regions Hospital. The study will primarily take place while the patient is in the ED, but the study intervention may take place in the ICU if the patient is quickly admitted. The ED pharmacists can oversee ICU medication orders, and the ICU pharmacists will also be trained about this study. This location is appropriate as this study is designed to assess the efficacy and safety of early basal insulin administration versus standard of care for the treatment of DKA. The department heads for endocrinology, emergency medicine, critical care, internal medicine and pharmacy were contacted and have endorsed providing support for this study. The Department of Endocrinology was consulted on providing recommendations for both the dosing of basal insulin as well as the timing of basal insulin initiation in relation to starting the IV insulin infusion. Furthermore, the ED pharmacists, ICU pharmacists, and floor pharmacists have a close working relationship, and communicate with each other daily. All three study investigators have spent time working as ICU pharmacists.

Due to the ongoing COVID-19 pandemic, additional actions will be taken to ensure the safety of patients and research staff. Research staff will follow the same PPE protocols as each patient's care team. Room entries for patient who have been ruled out for COVID will require a surgical mask. If a patient's COVID status is unknown, but COVID is not suspected, research staff will attempt to contact the patient via phone, or have a care team member who is entering the room for cares ask if the patient is interested in speaking with research, before entering the patient's room themselves. In this case, the research team will follow the same PPE routine as care team members who are entering the room. CCRC staff has permission to use PPE from the ED for research purposes. To reduce strain on ED PPE, CCRC staff has been instructed to retain N-95 masks and reuse for the equivalent of 5 full shifts per the current Worksite Health recommendation, and each CCRC staff member has their own reusable face shields. If the patient is COVID-positive, patients will not enter the patient's room, and will instead attempt to contact the patient via phone. If a paper consent form needs to be signed, a member of the care team in full PPE will bring it in to the patient at the time of other cares. Patients and LARs will be offered the option to sign a digital consent form, sent to their personal device via RedCap, as this will avoid a Research room entry.

### **Risks and Benefits**

Potential risks to the patient include hypoglycemia with the administration of both basal and regular insulin administration, however, no study that has examined early basal insulin in combination with IV insulin has shown an increase in the risk of hypoglycemia. Standard of care for patients with DKA includes an overlap of basal and regular insulin for approximately two hours; this ensures that the basal insulin has time to start working before stopping the regular insulin. In our study, patients will have a longer duration of overlap of basal and regular insulin as the basal insulin will be given earlier in the patient's treatment course. Patients with DKA who are receiving IV insulin

infusions, whether participating in this study or not, undergo frequent blood glucose monitoring and have the IV insulin infusion titrated appropriately to prevent hypoglycemia. Potential benefits to the patient and society include shorter hospital and ICU lengths of stay, faster time to resolution of DKA, and less rebound hyperglycemia.

For study patients randomized to the SOC group, the only potential for change in standard care would be if a provider who *would* have deviated from the Regions Hospital DKA Protocol were the patient not in the study *does not* deviate from it if the patient is in the study, due to education about the importance of adhering to the SOC DKA Protocol. (For example, a physician might give SC glargine before the patient meets all criteria for it in the DKA Protocol.) However, as the DKA Protocol is evidence-based, peer-reviewed, and created for optimal patient safety and outcomes, this should not be considered a risk. If, for whatever reason, a study patient in the SOC arm needs treatment that directly contradicts the SOC DKA Protocol, the patient will be withdrawn from the study to ensure patient care and safety are the first priority. In looking at existing data to inform this study protocol, only 3 of 45 patients with DKA at Regions Hospital received SC glargine prior to what the protocol dictates.

All adverse events and serious adverse events will be reported to the IRB within the required time windows.

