### Exclusion Criteria

- Age  $<$  18
- End stage renal disease or hepatic disease
- Hypotension requiring IV vasopressors or inotropes at any point during admission (i.e. norepinephrine, dobutamine, vasopressin, etc.)
- Need for emergent surgery
- Pregnant patients
- Prisoners
- Indication for insulin therapy other than DKA (hypertriglyceridemia, beta-blocker overdose, hyperglycemia without DKA)
- Patients receiving prior to admission insulin pump therapy
- Patients receiving prior to admission combination insulin products (i.e. Novolin® 70/30, Novolog® 70/30, Humalog® 75/25, etc.)
- Did not consent to study

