## **Screening and Enrollment**

### Screening

Because CCRC research interns provide 24/7 ED coverage, and ED pharmacy is also covered 24/7, there is no restriction as to the time of day or day of week when enrollments can take place. However, to enhance investigator oversight, patients will only be enrolled when specific ED Pharmacists are on shift, who are the primary investigators. This includes [name], [name], and [name]. If those pharmacists are not at the site, the patient will not be enrolled.

ED pharmacists received an Epic alert any time a patient meeting DKA criteria is admitted to the ED. The pharmacist will alert the CCRC research intern to confirm inclusion/exclusion and approach the patient for study participation. CCRC interns will also watch the ED track board for patients admitted with a chief complaint of DKA, nausea, vomiting, abdominal pain, hyperglycemia, or similar. Alternatively, an ED pharmacist or attending physician will notify Research of a potential patient by calling the 24/7 intern bat phone.

Labs: in order to confirm inclusion/exclusion criteria, the patient will need to have had the following labs completed (*which are standard of care for any patient with DKA on the differential diagnosis. These are not extra labs that the study investigators want, rather, they will already be collected by any provider for any patient with presumed DKA*):

- Arterial or venous pH  $\leq 7.3$
- Serum Bicarbonate  $\leq 18$  mEq/L
- Presence of ketonuria or ketonemia (beta-hydroxybutyrate  $> 0.27$  mmol/L)
- Anion Gap  $> 10$
- Blood sugar  $> 250$  mg/dL

All patients who present with symptoms of possible DKA should receive these labs under standard of care, per Regions Hospital DKA Protocol. Should any of these labs be missing, the patient will not be eligible for the study.

The research intern will confirm inclusion and exclusion criteria using a RedCap screening checklist, and obtain permission from the patient’s attending to approach for study consent.

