### Randomization

An Excel file with rows numbered 1 through 150 will be populated with a randomization column. Using Excel randomization functions, a research staff member who will not be involved in consenting will assign either the number 1 (control) or 2 (intervention) to each row number, ensuring 75 of each are populated. We chose the number 150 based on the expected sample size of 132, plus extras in case of higher-than-expected enrollment. The research staff member will then black out (black highlight over black font) the randomization column, so other team members are blinded to future assignments. Upon consent of an eligible patient, research staff will enter subject information in the next available row, and randomization status will be unblinded by removing the black highlight for that row only.

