### Enrollment

Once the patient is randomized, the CCRC intern will notify the ED pharmacist who will determine if patient is currently taking basal insulin and, if they are taking basal insulin prior to admission, will verify the home basal dosing. CCRC research staff will be notified of the dosing order from the randomization and will place the appropriate order. The patient will either receive 0.2 u/kg insulin glargine, current (prior to admission) basal insulin dose, or no additional treatment study protocol. CCRC staff will abstract the study data points from the patient’s EMR while the patient is in the Emergency Department, throughout their hospital stay, and again at the time of discharge. The ED pharmacist will time the insulin glargine dose to be administered optimally within two hours after initiation of the IV insulin infusion.

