### Variable list, sources, and data collection

The variables listed on the below data collection form will be incorporated into a secure REDCap database that research staff will use to enter the data. Patients will be assigned study ID numbers in the REDCap database. The REDCap database will contain identifying information, however, if de-identified data needs to be shared outside of the direct study team, the dataset can be downloaded without identifying variables such as MRN.

Variable Name	Role of Variable	Measurement Scale
Study ID	Unique identifier	Continuous (001 – n)
MRN	Link to EMR	String
Full name	Link to EMR	String
Date of ED presentation	Link to EMR	DMY
Age	Descriptive	Continuous
Race	Descriptive	Categorical, as reported in Epic
Ethnicity	Descriptive	Categorical, as reported in Epic
Sex at birth	Descriptive	Categorical, as reported in Epic
End stage renal disease or hepatic disease	Inclusion/exclusion criteria	Binary
Vasopressor dose to treat hypotension at any point during admission	Inclusion/exclusion criteria	Binary
On insulin pump therapy at baseline (prior to ED)	Inclusion/exclusion criteria	Binary
On combination insulin products (i.e. Novolin® 70/30, Novolog® 70/30, Humalog® 75/25, etc.) at baseline	Inclusion/exclusion criteria	Binary
Presenting pH (prior to intervention)	Inclusion/exclusion criteria	Continuous

Time of first pH	Calculate time to resolution	Continuous
Time of short-acting insulin start	Calculate time to resolution	Continuous
Time of first pH > 7.3	Outcome Calculate time to resolution	Continuous
Presenting blood glucose in mg/dL	Inclusion/exclusion criteria	Continuous
Time of first blood glucose < 250 mg/dL	Outcome Calculate time to resolution	Continuous
Blood glucose > 180 mg/dL in the 24 hours after IV insulin infusion discontinuation	Outcome	Binary
Blood glucose < 70mg/dL $\geq$ 1 time at any point while on IV insulin therapy or in the 24 hours after IV insulin infusion discontinuation	Outcome Prevalence of AE (hypoglycemia)	Binary
Blood glucose < 70mg/dL at any point between glargine start and 24 hours after IV insulin infusion discontinuation (control group only)	Outcome Prevalence of AE that may be contributable to study intervention (hypoglycemia)	Binary
Mean blood glucose in 24 and 48 hours after IV insulin infusion discontinuation	Outcome	Continuous
Presenting anion gap	Inclusion/exclusion criteria	Continuous
Time of first anion gap	Calculate time to resolution	Continuous

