### Statistical analysis plan

The primary outcome and secondary outcomes 1-4 and 7 will follow the same analysis plan to study the difference in the distribution of time to an endpoint. First, the distributions for each of these outcomes will be evaluated to determine if the distribution is normal or non-parametric. If the distribution is normal, that outcome will be analyzed using a two-tailed unpaired t-test. If the distribution is non-parametric, that outcome will be analyzed using a Wilcoxon rank sum test. We expect length of stay data to follow a non-parametric distribution. In secondary outcome 2, the outcome measured is the time at which all of the necessary criteria are hit for the first time simultaneously, which accounts for the transient nature of some of these measures.

Secondary outcomes 5-6 will measure the prevalence of each of these outcomes. Prevalence was chosen over incidence in order to account for multiple instances of rebound hyperglycemia or hypoglycemia occurring within the specified timeframe for each and also the amount of time it takes to clinically reverse these conditions. For both of these outcomes, a two-proportion z test will be run to find the difference in the amount of time each treatment arm cumulatively spent with the specified condition. Finally, for the outcomes relying on certain lab values, we will examine time from IV insulin infusion start to outcome labs in both groups. If there is significant variability between the experimental and SOC arms, we will adjust for this statistically. Group randomization should ensure that variability is

equally distributed between groups, however, there is a chance of bias (e.g., if the experimental group fares better and thus are slower to get nursing checks.)

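### Withdrawal after randomization applies to the SOC arm only and no analysis set is named, so the ICU-stay comparison is open to selection bias of unknown direction

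*Combined protocol and SAP*

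**What the plan says.** The Risks and Benefits section provides that if, for any reason, "a study patient in the SOC arm needs treatment that directly contradicts the SOC DKA Protocol, the patient will be withdrawn from the study", so that care and safety come first. This is the document's only rule for withdrawing a randomized patient, and it names one arm.

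The assignment is open by then. Under Randomization, once an eligible patient has consented, "randomization status will be unblinded by removing the black highlight for that row only". The Control group-specific section adds a consent note and a flag in the medical record that tell care teams about study participation.

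The Statistical analysis plan states that "The primary outcome and secondary outcomes 1-4 and 7 will follow the same analysis plan" and then chooses between a t-test and a Wilcoxon rank sum test. It names no analysis set, gives no intention-to-treat rule, and does not say whether a withdrawn patient's data are kept or dropped. Under Enrollment, abstraction from the medical record runs "throughout their hospital stay, and again at the time of discharge". That is written for patients in general and does not mention withdrawn ones.

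On frequency, Risks and Benefits reports from existing data that "only 3 of 45 patients with DKA at Regions Hospital received SC glargine prior to what the protocol dictates".

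A related item is the exclusion "Hypotension requiring IV vasopressors or inotropes at any point during admission". The variable list carries "Vasopressor dose to treat hypotension at any point during admission" as an eligibility variable. Yet eligibility is settled before consent: under Screening, "The research intern will confirm inclusion and exclusion criteria using a RedCap screening checklist".

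**The concern.** Randomization makes the arms comparable only while the same kinds of patient are counted in both. Here a patient whose course calls for treatment outside the hospital protocol leaves if assigned to SOC. A similar patient assigned to glargine stays in. If the ICU stays of the withdrawn controls differ from those of other controls, the control distribution shifts for reasons unrelated to treatment.

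The shift can go either way. Removing controls with long stays hides a benefit; removing controls with short stays creates one. The deviation that Risks and Benefits offers as an example is early SC glargine, which is the experimental treatment. If that is the treatment needed, the rule acts as a per-protocol exclusion of crossovers in one arm.

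There is a second risk. With no analysis set named, two analysts could each follow the plan and report different primary results, and the choice could be made after seeing data by arm.

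Ordinary provider deviations are not part of this point. The Control group-specific section handles them by education and flags.

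**Working it through.** **Inputs.** From the Sample size section: 66 per arm, ratio 1.31, coefficient of variation 0.6, alpha 0.05, power 80%. That section does not say whether the stay is ICU or hospital stay. From the Statistical analysis plan: a two-sided test, with Wilcoxon expected for length of stay. From Risks and Benefits: 3 of 45.

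**1. The plan's own figure.** Log-scale SD = sqrt(ln(1 + 0.6²)) = 0.5545. Standard error of the difference = 0.5545 × sqrt(2/66) = 0.0965. ln(1.31)/0.0965 = 0.2700/0.0965 = 2.80. Power = Φ(2.80 − 1.96), or 79.9% (79.3% by noncentral t). The stated 80% reproduces. The Wilcoxon test, by simulation, has 77%.

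**2. How many controls could be affected.** 3/45 = 6.7%, exact (Clopper-Pearson) 95% CI 1.4% to 18.3%. Times 66: 4.4 patients, range 0.9 to 12.1. This proxy is an assumption.

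**3. Loss of numbers alone.** Removing 4 controls at random takes t-test power from 79.3% to 78.0% and leaves type I error at 4.9% (Wilcoxon). Numbers are not the problem; selection is.

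**4. Selective removal, normal theory.** Let a fraction f of both arms have stays m times those of the rest, and remove that fraction from controls only. The difference in mean logs moves by f × ln(m). With f = 0.0667 and m = 2: 0.0667 × 0.693 = 0.046, or 0.046/0.0965 = 0.48 standard errors. Power = Φ(2.80 − 0.48 − 1.96) = 64%. With m = 0.5 the shift reverses and type I error is Φ(−1.96 + 0.48) + Φ(−1.96 − 0.48), about 8%. With m = 1.25, power is 75% and type I error 5.3%.

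**5. Selective removal, planned Wilcoxon test.** Log-normal stays, 66 per arm, 40,000 simulated trials per cell. The kept figures in the last two rows come from separate repeat simulations. Repeats agreed within about 1 point. Power is at ratio 1.31.

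| Share removed from controls | Stay relative to the rest | Power, dropped | Power, kept | Type I error, dropped |
|---|---|---|---|---|
| 6.7% | equal | 76% | 77% | 5.0% |
| 6.7% | 1.25-fold | 71% | not run | 5.1% |
| 6.7% | 1.5-fold | 66% | not run | 5.8% |
| 6.7% | 2-fold | 59% | 73% | 7.0% |
| 6.7% | half | 85% | 74% | 7.0% |
| 1.4% | 2-fold | 74% | 76% | 4.9% |
| 18.3% | 2-fold | 27% | about 69% | 19% |

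In the half-stay case, a repeat simulation put false positives favoring glargine at 5.8%, against a nominal 2.5%.

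**6. Outer bounds with 4 controls removed and no true effect (Wilcoxon).** Dropping the 4 longest SOC stays moves the SOC/glargine geometric mean ratio from 1.00 to 0.93, with type I error 9.9%. Dropping the 4 shortest moves it to 1.07, with 9.5%. Dropping 4 at random from the upper or lower half gives 0.97 or 1.03, with about 6%.

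**The case against.** The strongest reply is that nothing says the data are discarded. The rule sits in a safety section, and the Enrollment section has records abstracted to discharge without exception. On that view the plan is silent rather than biased. The silence is real, and the bias does depend on exclusion. But leaving the study is the ordinary meaning of the words, and nothing provides for keeping or analyzing these patients. A general statement about abstraction does not settle the analysis.

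Second, the rate is borrowed. The 3 of 45 received early glargine outside the trial, which is the behavior that education is meant to reduce. The documents give no rate for patients who need contradictory treatment. The true count could be zero, or higher if other treatments trigger the rule. This stands, so the figures are illustrations and not forecasts.

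Third, the likely effect is modest. With 1.25-fold stays, type I error is 5.1%. The 27% power and 19% type I error need both the upper confidence limit of a proxy and doubled stays, and the fair comparison there is about 69% with patients kept, not the 77% baseline. This also stands as to size. It does not excuse leaving a one-arm rule and an undefined analysis set in a confirmatory comparison.

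Fourth, the vasopressor item is weaker. It applies to both arms, no text orders removal of a randomized patient, and no rate is given. It needs clarifying only.

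**Conclusion.** The concern holds, with high confidence as to the text. The plan states a post-randomization withdrawal rule for one arm, applied with the assignment known, and gives no analysis set that would keep those patients in the primary comparison.

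The size is uncertain. It rests on three assumptions: that withdrawn means excluded from analysis, that the proxy rate is roughly right, and how the withdrawn patients' stays compare with the rest. The effect runs from almost nothing, if stays are equal, to a clear loss of power or an inflated false-positive rate. The direction cannot be fixed from the documents. This must be fixed because it touches the primary result and because outcomes not collected after withdrawal may not be recoverable.

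**What to change.** - State in the Statistical analysis plan that the primary analysis includes every randomized patient in the assigned arm.
- In Risks and Benefits, separate leaving protocol-directed care from leaving the study. Outcome data continue to be abstracted from the medical record and are analyzed as randomized, unless the patient withdraws consent to data use. Clinical care decisions are unchanged.
- State that the vasopressor criterion is judged on what is known at randomization, and that later use does not remove a patient from the analysis.
- Report deviations and withdrawals by arm, with reasons. Use a per-protocol analysis as a sensitivity analysis only.

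The change is wording only, since abstraction to discharge is already planned. The cost is dilution: controls who receive early glargine and are kept bring the arms closer together. If 6.7% cross over with the full effect (assumed), the ratio falls to exp(0.9333 × ln 1.31) = 1.29. Power is then about 74% on logs (from about 80%) or 71% with Wilcoxon (from 77%). The fix protects validity; it does not restore 80% power.
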